***Please place the following information in the Patient Registration Window before the exam begins:**

- Place with the study ID number (PID) in the MRN Field.
- Place the acrostic in the Patient Name Field.
- These should be given to you by the Study Coordinator.

General Overview

This is a cardiovascular MR exam that acquires baseline imaging (pre-exercise stress test) with a peak CPET test performed in the MRI facility. Patients are escorted from the CPET test to the MRI table with auto-scanning enabled for MRI measures of post-exercise stress test beginning <20 seconds after peak exercise. Recovery LV cines are acquired after the heart rate has normalized to ensure no wall motion abnormalities were induced with stress testing.

Improving Exercise Capacity with a Tailored Physical Activity Intervention in Lymphoma and Breast Cancer Patients Undergoing Treatment – An addendum to NIH
R01CA167821 “Early Imaging Detection of CV Injury after Cancer”
Comprehensive Cancer Center of Wake Forest University (CCCWFU- #99112)

MRI Protocol – List of Sequences

BASELINE (Pre-Exercise)
Localizers
3 PLANE LOC BH
2CH LOC FB
SAX LOC FB
4CH LOC FB
LAO SCOUT FB
ABD LOC
Body Composition
T1 AX ABDOMEN FAT (L2-L4)
Axial Phase Contrast
BASELINE AX Aorta Arch 2D PHASE CONTRAST
BASELINE AX Aorta Bifur 2D PHASE CONTRAST
Fast Cines
BASELINE_SAX_CINE_RT (GATED) (Slices to cover the entire LV)
***POST CPET EXERCISE ***
Fast Cines
EXERCISE_SAX_CINE_RT (GATED) (Slices to cover the entire LV)
Axial Phase Contrast
exercise AX Aorta Arch 2D PHASE CONTRAST
exercise AX Aorta Bifur 2D PHASE CONTRAST
RECOVERY
Fast Cines
RECOVERY_SAX_RT (GATED) (Slices to cover the entire LV)

Participant Preparation

1. Complete the MRI safety screening form required at your institution. All participants must be screened for MRI safety/compatibility.
2. Request participant use the rest room before the study.
3. Breath-holding is done at resting lung volume for the entire protocol.
 - a. Test breath-holding. **The participant is required to be able to hold their breath for 15 seconds at resting lung volume twice in order to participate in the protocol.**
 - b. Inform and train participant on breath-holding, example: “Breath in ... Let your air out until you are comfortable, and stop breathing.”
4. Make sure that the connectors for cardiac coils and ECG are in place.
5. Remember to place nonferromagnetic brachial blood pressure cuff on participant’s arm prior to beginning the MRI scans. This is needed to record blood pressures during certain sequences as marked on the encounter form.

Thoroughly clean the ECG contact area with alcohol swabs. With participant supine on the table, attach ECG electrodes to his/her chest according to your MRI manufacturer suggestions.

Image Acquisition

MRI encounter form

Complete the MRI encounter form during each scan and complete the notes regarding sedation/completion of study. ***The encounter form is included in the last page of this appendix.***

It is recommended that this form is completed in real-time during the study to ensure no sequences are skipped and the blood pressures and heart rates are recorded as necessary.

Improving Exercise Capacity with a Tailored Physical Activity Intervention in Lymphoma and Breast Cancer Patients Undergoing Treatment – An addendum to NIH R01CA167821 “Early Imaging Detection of CV Injury after Cancer”
Comprehensive Cancer Center of Wake Forest University (CCCWFU- #99112)

Series Name: _3_PLANE_SCOUT

[figure not shown]
[figure not shown]
Series Description: 3 Plane Localizer

Notes: Steady-state free precession scout images

Series Prescription Details

	Series Rx Notes
Prescribe series from:	Localize the heart at the isocenter.
Orientation:	three orthogonal planes (axial, coronal and sagittal)
Number of Slices	At least three slices per plane (at least 9 image
Breath-holding:	Yes, resting lung volume

Sample Images

[figure not shown]
Improving Exercise Capacity with a Tailored Physical Activity Intervention in Lymphoma and Breast Cancer Patients Undergoing Treatment – An addendum to NIH R01CA167821 “Early Imaging Detection of CV Injury after Cancer”
Comprehensive Cancer Center of Wake Forest University (CCCWFU- #99112)

Series Name: 2CH LOC FB

[figure not shown]
Series Description: White-blood 2 Chamber localizer; Pseudovertical long-axis localizer

Notes: This is a bright-blood steady-state free precession, one slice (non-cine) image.

Series Prescription Details

	Series Rx Notes	Sample Series Rx
Prescribe series from:	Plan this on the axial scout view (_3_PLANE_SCOUT) with the largest volume of heart, from the base (middle of the mitral valve) to apex of the LV, on the axial scouts.	
Orientation:	Oblique	
Number of Slices	1	
Breath-holding:	No	

Sample Image

[figure not shown]
Improving Exercise Capacity with a Tailored Physical Activity Intervention in Lymphoma and Breast Cancer Patients Undergoing Treatment – An addendum to NIH R01CA167821 “Early Imaging Detection of CV Injury after Cancer”
Comprehensive Cancer Center of Wake Forest University (CCCWFU- #99112)

Series Name: **SAX LOC FB**

[figure not shown]
Series Description: White-blood short-axis localizers

Notes: These are a bright-blood steady-state free precession, non-cine images covering the whole heart from great arteries to the apex. Data acquisition at the **diastolic phase**.

Series Prescription Details

	Series Rx Notes	Sample Series Rx
Prescribe series from:	2CH_LOC cross-referenced with 4CH_LOC	
Orientation:	Oblique	
Number of Slices	12	
Breath-holding:	No	

Sample Images

[figure not shown]
Series Name: **4CH LOC FB**

Improving Exercise Capacity with a Tailored Physical Activity Intervention in Lymphoma and Breast Cancer Patients Undergoing Treatment – An addendum to NIH R01CA167821 “Early Imaging Detection of CV Injury after Cancer”
Comprehensive Cancer Center of Wake Forest University (CCCWFU- #99112)

[figure not shown]
Series Description: White-blood 4 Chamber localizer; horizontal long-axis localizer

Notes: This is a bright-blood steady-state free precession, one slice (non-cine) image.

Series Prescription Details

	Series Rx Notes	Sample Series Rx
Prescribe series from:	Plan this on the axial scout view (_3_PLANE_SCOUT) with the largest volume of heart, from the base (middle of the mitral valve) to apex of the LV, on the axial scouts. Cross-reference with 2CH Scout	
Orientation:	Oblique	
Number of Slices	1	
Breath-holding:	No	

Sample Image

[figure not shown]
Improving Exercise Capacity with a Tailored Physical Activity Intervention in Lymphoma and Breast Cancer Patients Undergoing Treatment – An addendum to NIH R01CA167821 “Early Imaging Detection of CV Injury after Cancer”
Comprehensive Cancer Center of Wake Forest University (CCCWFU- #99112)

Series Name: LAO_SCOUT_FB

[figure not shown]
Series Description: Aorta candy cane localizer, free-breathing

Notes: This localizer is a left anterior oblique in the candy cane plane of the thoracic aorta. This multi-slice localizer will be used for planning the aorta phase contrast images.

Series Prescription Details

	Series Rx Notes	Sample Series Rx
Prescribe series from:	_3_PLANE_SCOUT axial image with ascending and descending aorta	
Orientation:	Left anterior oblique; plane center slice through ascending and descending aorta	
Number of Slices	6-8	
Breath-holding:	No	

Sample Image(s)

Improving Exercise Capacity with a Tailored Physical Activity Intervention in Lymphoma and Breast Cancer Patients Undergoing Treatment – An addendum to NIH
R01CA167821 “Early Imaging Detection of CV Injury after Cancer”
Comprehensive Cancer Center of Wake Forest University (CCCWFU- #99112)

Series Name: **ABD_LOC**

Series Description: Abdominal Localizer

Notes: Perform multi-plane abdominal localizer (coronal and sagittal); Siemens sequence name = tfl2d1_84. A coronal plane that appreciates the aorta bifurcation will be used in planning future series. A sagittal plan that appreciates L2-L4 will be used in planning future series.

Series Prescription Details

	Series Rx Notes
Prescribe series from:	3_PLANE_SCOUT
Orientation:	Coronal and Sagittal
Number of Slices	3-5 sagittal slices; 8-10 coronal slices
Breath-holding:	Yes

Image Parameters

Image Parameter	Value
Slice Thickness	5mm
Slice Gap	5 mm
TR	260
TE	1.08
Number of Phase Encodings	143
Percent Sampling	75 %
Percent Phase FOV	100%
Pixel Bandwidth	1132
Matrix	192 x 144
Flip Angle	65 degrees

Sample Images:

Improving Exercise Capacity with a Tailored Physical Activity Intervention in Lymphoma and Breast Cancer Patients Undergoing Treatment – An addendum to NIH R01CA167821 “Early Imaging Detection of CV Injury after Cancer”
Comprehensive Cancer Center of Wake Forest University (CCCWFU- #99112)

Improving Exercise Capacity with a Tailored Physical Activity Intervention in Lymphoma and Breast Cancer Patients Undergoing Treatment – An addendum to NIH
R01CA167821 “Early Imaging Detection of CV Injury after Cancer”
Comprehensive Cancer Center of Wake Forest University (CCCWFU- #99112)

Series Name: **T1_AX_ABDOMEN_FAT**

Series Description: T1 weighted turbo spin-echo sequence acquired with 3 evenly spaced axial slices with 1st and 3rd centered at L2 and L4.

Notes: To assess visceral fat, a series of images will be acquired to assess visceral fat volume. Open up FOV to encompass all of the abdomen.

[figure not shown]
[figure not shown]
Series Prescription Details

	Series Rx Notes	Sample Series Rx
Prescribe series from:	Sagittal plane on ABD_LOC	
Orientation:	Axial	
Number of Slices	3 - evenly spaced axial slices with 1 st and 3 rd centered at L2 and L4.	
Breath-holding:	Yes	

Image Parameters

Image Parameter	Value
FOV	Open to encompass all of the abdomen
Slice thickness (mm)	5mm
Slice gap (mm)	Variable – change distance factor as necessary
TR	800 ms
TE	36 ms
Flip angle (degrees)	180
Matrix	256 * 256
Acceleration factor	2
Bandwidth	305 Hz/Px
Turbo factor	11
Echo trains per slice	13
Gating	ECG triggering

Sample Image(s)

Improving Exercise Capacity with a Tailored Physical Activity Intervention in Lymphoma and Breast Cancer Patients Undergoing Treatment – An addendum to NIH
R01CA167821 “Early Imaging Detection of CV Injury after Cancer”
Comprehensive Cancer Center of Wake Forest University (CCCWFU- #99112)

Series Name: **AX Aorta Arch 2D PHASE CONTRAST**

AX Aorta Bifur 2D PHASE CONTRAST

Series Description: ***Free breathing***, 2D Phase Contrast images of the aorta in 2 planes: the ascending-descending aorta at the level of the arch and at the level of 2 cm above the bifurcation.

Notes: Phase-contrast gradient-echo images will be acquired in axial planes for determination of aortic stiffness. Measures of distensibility and pulse wave velocity will be performed on the phase-contrast images. **Roughly 30 phases should be acquired.** This is performed at baseline and again post-exercise (following LV Cine stack).

[figure not shown]
Series Prescription Details - AX Aorta Arch 2D PHASE CONTRAST

	Series Rx Notes	Sample Series Rx
Prescribe series from:	Prescribe off of the LAO_SCOUT_FB images and select the slice with the best view of the aorta candy cane. Prescribe an oblique plane running perpendicular through the ascending and descending aorta as shown on the right.	
Orientation:	Axial; oblique	
Number of Slices	1	
Breath-holding:	No	

Series Prescription Details - AX Aorta Bifur 2D PHASE CONTRAST

	Series Rx Notes	Sample Series Rx
Prescribe series from:	Prescribe off of the ABD_LOC images and select the slice with the best view of the aortic bifurcation. Prescribe a plane running perpendicular through the aorta at the level 2 cm	

Improving Exercise Capacity with a Tailored Physical Activity Intervention in Lymphoma and Breast Cancer Patients Undergoing Treatment – An addendum to NIH
 R01CA167821 “Early Imaging Detection of CV Injury after Cancer”
 Comprehensive Cancer Center of Wake Forest University (CCCWFU- #99112)

	superior to the bifurcation as shown on the right.	
Orientation:	Axial	
Number of Slices	1	
Breath-holding:	No	

Ph Con Image Parameters

[figure not shown]
[figure not shown]
Image Parameter	Siemens	GE	Philips
Coil	Body Matrix	Gore Full	Cardiac
Plane	Oblique	Oblique	Axial
Field of View	360	360	360
Repetition Time (TR; ms)	12.0	12.0	12.0
Echo Time (TE; ms)	3.14	Min	2.8
Flip Angle (degrees)	15	30	12
Averages	1		1
BW	389	31.25	477.8
NEX		1.00	1
Gated	Cardiac	Cardiac (auto # phases, TrigWin 10)	Retrospective
Sequence type	Phase-contrast GRE	Phase-contrast GRE	2D FFE
Axial Velocity encoding direction	Through-plane	Through-plane	Through-plane
Parasagittal Velocity encoding direction	Head-Foot or Superior-Inferior	Head-Foot or Superior-Inferior	Head-Foot or Superior-Inferior
Slice Thickness	6 mm	6	6
Distance Factor	20% (1.2m)		
Segments	6		
Matrix	128 x 128	128 x 128	128x128
Phase FOV	100%	1.00	100%

Improving Exercise Capacity with a Tailored Physical Activity Intervention in Lymphoma and Breast Cancer Patients Undergoing Treatment – An addendum to NIH
 R01CA167821 “Early Imaging Detection of CV Injury after Cancer”
 Comprehensive Cancer Center of Wake Forest University (CCCWFU- #99112)

[figure not shown]
Phase encode direction	A-P	A-P	A-P
Phases	20	20	20
PSD		Vasc PC (Fast 2D Phase Contrast	
Options		Gat, Seq, Fast	
Flow Comp		Off	Yes
Gap		0	0
VPS		2 (adjust per patient's heart rate for ~30 phases)	
Frequency		S/I	
Grad Mode		Whole	Default
VENC	Start with 200, may increase if aliasing	200	200
Vascular Screen		Venc: 200, Collapse: off, Recon: Ph Diff, Flow Analysis: on, Flow Dir: Slice, Additional Images: Obl S/I	
User CV Screen		All set to zero	Turn off Complex Difference

Ph Con Sample Image(s)

Resulting magnitude (top row) and velocity maps (bottom row) images

Improving Exercise Capacity with a Tailored Physical Activity Intervention in Lymphoma and Breast Cancer Patients Undergoing Treatment – An addendum to NIH
R01CA167821 “Early Imaging Detection of CV Injury after Cancer”
Comprehensive Cancer Center of Wake Forest University (CCCWFU- #99112)

Series Name: **SAX_CINE_RT (GATED)** – Performed at baseline, post exercise, and recovery

Series Description: Fast short axis cine stack encompassing LV with ECG gating

Notes: **** Record BP and HR during acquisition ****

[figure not shown]
This is real-time, cardiac triggered, free-breathing cine stack acquired in the SAX plane with minimum of 20 phases, covering the whole heart from the atria_to apex. Temporal resolution should be <40 ms. Cine short axis images should be obtained at baseline, immediately following exercise, and when heart rate recovers to <100 bpm.

Parallel imaging (e.g. ASSET, SENSE, or GRAPPA) with an acceleration factor of 2 to reduce acquisition time (optional). Flip angle should be set at the largest possible (usually 45-70°). The last apical slice should locate within the myocardium such that the slices could cover left atrium as much as possible.

Series Prescription Details

	Series Rx Notes	Sample Series Rx
Prescribe series from:	4 Ch Loc and SAX Loc.	
Orientation:	SAX Oblique	

Improving Exercise Capacity with a Tailored Physical Activity Intervention in Lymphoma and Breast Cancer Patients Undergoing Treatment – An addendum to NIH R01CA167821 “Early Imaging Detection of CV Injury after Cancer”
Comprehensive Cancer Center of Wake Forest University (CCCWFU- #99112)

Number of Slices	As needed to cover apex to atria with slice thickness = 8 mm and slice gap = 2mm.	
Breath-holding:	No	

Improving Exercise Capacity with a Tailored Physical Activity Intervention in Lymphoma and Breast Cancer Patients Undergoing Treatment – An addendum to NIH R01CA167821 “Early Imaging Detection of CV Injury after Cancer”

Comprehensive Cancer Center of Wake Forest University (CCCWFU - #99112)

CPET Stress MRI Encounter Form

Date of scan: _____ Tech: _____ Time: _____ Visit #: _____ Height: _____ inches Weight: _____ lb	Participant Name/MRN and Study ID / Label Here		
BASELINE	Series#	Record INVIVO BP/HR(MRITech)	INVIVO STRIP HR (Nurse)
Localizers		BP: _____ / _____ HR: _____	HR: _____

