Figure 7: Upright Treadmill Exercise CMR-CPET Stress Test Protocol. (a) CMR scanner with shoulder harnesses (black arrows) to aid with correct patient/participant positioning (b) obtaining rest cine imaging; (c) placement of electrode patches and blood pressure cuff for patient monitoring; (d) treadmill exercise stressing with expired gases, and (e) repositioning the patient/participant into the scanner for post-stress cine images.

escorted into the scanner to allow researchers to collect resting CMR images (Figure 7). Upon completion, the participant then will perform a CPET, according to the Bruce or Modified Bruce protocol. When the individual indicated they were at their maximal capacity the test will be terminated and the subject will be immediately escorted quickly back into the scanner to collect immediate post exercise CMR measures. In our pilot data and in our publications, all post-exercise CMR data are initiated 20 seconds after exercise completes and acquisitions are completed within 50 seconds of leaving the treadmill. After the post exercise CMR is completed, the individual will be monitored to ensure that HR falls to <100 bpm during which recovery LV wall motion assessments will be made. All images will be acquired using the Siemens 1.5 Tesla Avanto scanner located in the Cardiovascular Imaging Center (Reynolds Tower, Wake Forest Health Sciences, Winston-Salem, North Carolina).

The CMR protocol is performed according to prior techniques⁴⁸⁻⁵⁰ & includes a series of white blood steady-state free precession cine images acquired in the short-axis plane to cover the entire left ventricle (LV) using a 5 to 10 second real-time, cardiac-gated, free breathing acquisitions with the following parameters: 6-10 slices of 8 mm thickness and 2 mm gap spanning the entire LV, a 128x72 matrix, a 340 x 255 mm field of view, 72 views per segment with view sharing, and echo spacing of 2.1 ms, resulting in a temporal resolution of 46 ms and voxel size of 2.6 x 2.6 x 8 mm. From these images, LV end-diastolic (LVEDV) and end-systolic (LVESV) volumes will be determined for calculation of the LV ejection fraction and stroke volume. Identical sets of volumetric images were acquired pre-exercise and post-exercise (<30 sec from maximal exercise stress test).

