There is a slight burden of using the technology to complete these tests, though all our participants are required to have a smart phone in order to sync their tracking devices regularly and we do not expect the level of expertise needed here is more than already required. Included in the instructions are links to short video clips demonstrating the procedures for clarity.

The participants may contact us at any time throughout the procedures.

Once testing is complete will ask the participants to send back the locked container using a pre-addressed shipping label. This can be picked up by the shipper if the participant does not feel safe. Finally, upon receipt of the materials all equipment will be sanitized with medical grade cleaners.

Blood testing. With each study visit, serum hemoglobin/hematocrit will be obtained to assess for the presence of anemia, and serum chemistries will be obtained to assess serum creatinine to identify renal dysfunction. Additionally, at baseline, 3 & 6 months, blood will be obtained for long-term storage of serum and plasma for future studies. Planned studies include assessments of markers of inflammation and CV injury.

Database management

All data management activities will be accomplished through a secure web-based Oncore application managed and administered by the CCCWFUHS (see

Improving Exercise Capacity with a Tailored Physical Activity Intervention in Lymphoma and Breast Cancer Patients Undergoing Treatment – An addendum to NIH
R01CA167821 “Early Imaging Detection of CV Injury after Cancer”
Wake Forest Baptist Comprehensive Cancer Center
CCWFU# 99112

Resources – [name], Jr.). This system allows flexibility in processing data management tasks, including the ability to register participants and verify eligibility criteria before randomization, provide the randomization assignment, and allow real-time monitoring and reporting of accrual, retention, and intervention adherence.

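### Appendix C makes two 15-second breath-holds a condition of taking part, although the outcome scans are free-breathing and the condition is not an eligibility criterion; this can cost enrolled patients imaging that was obtainable

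*Combined protocol and SAP*

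**What the plan says.** Appendix C, Participant Preparation, tells the MRI technologist to test breath-holding and states that patients are "required to be able to hold their breath for 15 seconds at resting lung volume twice in order to participate in the protocol". The item above it reads "Breath-holding is done at resting lung volume for the entire protocol".

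The series that yields LV volumes, ejection fraction, stroke volume and cardiac output is described differently. Appendix C, under SAX_CINE_RT, says "This is real-time, cardiac triggered, free-breathing cine stack acquired in the SAX plane with minimum of 20 phases". Section 5.2 (MRI Variables) says the cines are obtained "using a 5 to 10 second real-time, cardiac-gated, free breathing acquisitions".

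Section 3.0 illustrates MRI contraindications with metal and implanted devices and does not mention breath-holding. Appendix B has a general MRI contraindication item and no breath-hold item. Section 5.1.2 and the Analytic Plan (6.0) make the proportion of all patients, in both arms, who can have the baseline and follow-up cardiovascular imaging part of the primary feasibility outcome. Neither says how a patient who fails the breath-hold test is counted.

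**The concern.** The condition tests a skill that the outcome scans do not need. A patient who can lie in the scanner and breathe freely could provide every LV measure named in Section 5.2, yet be turned away for failing a 15-second hold. These patients are receiving cancer treatment, so some who pass at baseline may not pass at 3 or 6 months.

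The imaging proportion is meant to tell the designers of the larger trial whether exercise MRI can be done in this population. If part of any shortfall comes from a rule in the imaging manual, the pilot will report a limitation that the method does not have. Because the checklist has no field for this reason, losses before randomization would also be hard to identify when the reasons for failed randomization are reported (objective 2.1.1).

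**Working it through.** **1. Which series need a breath-hold (Appendix C series tables)**

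| Series | Breath-hold | Role |
|---|---|---|
| 3-plane scout | Yes ("Yes, resting lung volume") | Planning |
| 2-chamber, short-axis, 4-chamber and LAO localizers | No | Planning |
| Abdominal localizer (ABD_LOC) | Yes | Planning |
| T1 abdominal fat | Yes | Visceral fat, not among the outcomes in 5.1 or 5.2 |
| Aortic phase contrast, arch and bifurcation | No | Aortic stiffness |
| Short-axis cine: baseline, post-exercise, recovery | No | LV volumes, ejection fraction, stroke volume, cardiac output |

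No series that supplies an LV outcome is breath-held.

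**2. When the test happens**

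Appendix C has the technologist enter the study ID, supplied by the coordinator, before the exam begins. Section 4.2 has the registrar assign the study number at registration, and Appendix A requires signed consent before that. The patient at the scanner is therefore already consented and registered. Section 5.2 repeats the measures at 3 and 6 months, and the encounter form carries a visit number and is completed at each scan. Nothing limits the preparation steps to baseline, so the test recurs. A patient who passes at baseline and fails later cannot be a screen failure.

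**3. What depends on the breath-held localizers**

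- The 2-chamber, 4-chamber, LAO and abdominal localizers are prescribed from the 3-plane scout. The short-axis localizer is prescribed from the 2- and 4-chamber views, and the outcome cine from the 4-chamber and short-axis localizers. The cines therefore trace back to the scout.
- The bifurcation phase-contrast series is prescribed from ABD_LOC: "A coronal plane that appreciates the aorta bifurcation will be used in planning future series".

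Of the three breath-held series, only the fat series can be lost without affecting another.

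**4. Size**

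The point rests on no figure in the plan. The precision that Section 6.0 states for this proportion at 21 patients (0.211 to 0.789, width 0.578) does not reproduce. The exact width is 0.445 at 10/21 (0.257 to 0.702) or 11/21 (0.298 to 0.743), and the printed interval is that for 6/12. That is a separate matter, but it is why the Clopper-Pearson intervals below are computed afresh.

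Input from the plan: n = 21. Assumed: k patients fail the hold and every other patient is imaged.

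If failures stay in the denominator, the proportion is (21 − k)/21:

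| k (assumed) | Proportion | 95% exact interval |
|---|---|---|
| 0 | 21/21 = 100% | 0.839 to 1.000 |
| 1 | 20/21 = 95.2% | 0.762 to 0.999 |
| 2 | 19/21 = 90.5% | 0.696 to 0.988 |
| 4 | 17/21 = 81.0% | 0.581 to 0.945 |

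Each failure costs 1/21 = 4.8 points. If the same patients are turned away before enrolment and replaced, or left out of the denominator, the proportion stays at 100%.

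More generally, with failure share f and completion share c among the rest, the proportion is (1 − f)c when failures are kept and c when they are removed. For an assumed c = 0.90:

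- f = 5%: 0.95 × 0.90 = 0.855, against 0.90
- f = 10%: 0.90 × 0.90 = 0.81, against 0.90
- f = 20%: 0.80 × 0.90 = 0.72, against 0.90

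**The case against.** Appendix C is an imaging manual for technologists, so the protocol that a patient must qualify for may well be the MRI exam and not the study. This stands. A reader might infer that the rule bars people from the trial, and the documents do not establish that. The narrower reading still leaves the problem: the patient stays in the study, loses the imaging, and is among the patients whom 5.1.2 counts.

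The line about the entire protocol may only fix the lung volume to use whenever a hold is called for, since the sequence list itself labels series as breath-held or free-breathing. That is a fair reading. It makes this line a matter of clarity, but the 15-second condition is a separate sentence and is not softened by it.

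A reader might also infer that the rule does lower the feasibility proportion. The documents do not support that as a fact. The effect depends on when patients fail and how they are counted, neither of which is stated. If they are removed before enrolment, the proportion is unchanged, or is overstated for the population that Section 3.0 defines. No failure rate is given, so the effect may be nil.

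Section 3.0 has a relative exclusion, at the medical director's discretion, for conditions that could prevent completion. It could be used for such patients, but it does not name breath-holding and is discretionary, whereas the Appendix C rule is absolute.

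Finally, breath-holding is not redundant: three baseline series use it and two of those are needed to plan later scans. This stands and shapes the fix.

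**Conclusion.** The concern holds as an unlisted condition that is at odds with the acquisition method of the outcome scans, coupled with a missing counting rule. Because the test falls on registered patients and recurs at follow-up, the rule can lower the primary imaging proportion for a reason unrelated to whether the outcome scans can be obtained. The size is 4.8 points per affected patient, assuming that the patient would otherwise have been fully imaged and stays in the denominator of 21. The number affected is unknown and may be zero, and the direction reverses or vanishes if failures are removed before enrolment. It is a wording correction worth making because it protects a primary measure in a small pilot.

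**What to change.** In Appendix C, Participant Preparation, reconcile the breath-hold items with the series tables and with Section 5.2:

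- Remove the condition on participation, and attempt the free-breathing cine and phase-contrast series in every patient at every visit.
- Apply the breath-hold requirement to the abdominal fat series only, and record that series as missing if the hold fails.
- State that the 3-plane scout and ABD_LOC are still acquired when the 15-second hold fails, for example free-breathing as the other localizers already are, because later series are planned from them.
- Reword the item on resting lung volume so that it clearly refers to the series that use a hold.

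If the sponsor prefers to keep the condition, list it in Section 3.0 and Appendix B, test it before enrolment, and state in 5.1.2 and Section 6.0 that a patient who fails later stays in the denominator and counts as not imaged.

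The cost of the preferred change is a few sentences in Appendix C, some missing abdominal fat images and possibly lower-quality localizers. The outcome scans are acquired by the same method as before.
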